9.3.3. Prescribed daily dose and duration of tofacitinib therapy

To assess utilization patterns, prescribed daily dose (DD) and duration of tofacitinib therapy will be described using days of supply and amount dispensed for patients who are prescribed tofacitinib for on-label, off-label and unknown indications.

Duration of tofacitinib therapy will be defined as the time from the date of the first ever tofacitinib prescription to the date of discontinuation of tofacitinib. The operational definitions for duration of tofacitinib therapy will be further elaborated in the SAP.

Prescribed DD will be calculated in milligrams per day, starting from the index date and using reported days' supply and dispensed amount, and will be stratified by indication for tofacitinib use, classified as on-label, off-label, or unknown. Further details will be provided in the SAP. DD will be time-varying and reported as a continuous and categorical variable:

- Up to 5 mg ADD;
- >5 mg to 11 mg ADD;
- >11 mg to 15 mg ADD;
- >15 to 20 mg ADD; and
- >20 mg ADD.

To assess patients' tofacitinib dose while on maintenance therapy, tofacitinib maintenance dose will be defined as patients' tofacitinib dose post 16 weeks of the patient's first ever tofacitinib prescription (i.e. patient's recorded tofacitinib dose at ≥Week 17 after patient's first ever tofacitinib prescription).

9.3.4. Index Date

9.3.4.1. Drug Utilization Study

For the drug utilization portion of the study, the date of the first prescription of tofacitinib during the study period is the index date.

9.3.4.2. Active Surveillance Study

For the active surveillance portion of the study, index date will be defined as follows:

Cohort 1: This will be the date of first prescription for tofacitinib since 30 May 2018, following a diagnosis of UC as described in Section 9.2.1.2.1.

Cohort 2: This will be the date of first prescription for a specific biologic agent since 30 May 2018, following diagnosis of UC as described in Section 9.2.1.2.2. For patients with more than one biologic initiation, more than one index date will be defined (e.g., one for each biologic initiation).

Cohort 3: This will be the date of first prescription for a specific immunomodulator/immunosuppressant agent since 30 May 2018, following diagnosis of UC as described in Section 9.2.1.2.3. For patients with more than one immunomodulator/immunosuppressant initiation, more than one index date will be defined.

Cohort 4: This will be the date of UC diagnosis as described in Section 9.2.1.2.4, since 30 May 2018.

[figure not shown]

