9.2.1.2. Active surveillance study

The active surveillance population to be used for the estimation of the incidence rates of the safety events of interest will be a subset of the population described above, and will include all adult UC patients aged ≥18 years who are enrolled in the Marketscan database from the time of approval of tofacitinib for UC in the US (May 2018) through to the end of data collection (June 2025) for the study. UC patients will be identified via ICD-10 codes listed in Table 1. Using all available data, UC patients must have at least one UC diagnosis code from an inpatient visit, or at least two occurrences of a UC diagnosis code from outpatient vists, with at least one of the two outpatient codes documented by a gastrointestinal specialist. UC codes assigned on different dates do not need to be the same to qualify. At least 12 months of continuous (i.e., no more than a 30-day gap) database enrollment before index date is required to enable analysis of baseline patient and disease characteristics that may be important modifiers of the relationship of UC with safety endpoints of interest. Index date is defined in the treatment cohort inclusion criteria listed in the subsections below.

ICD-9 Code	Diagnosis	ICD-10 code	Diagnosis
556 (no 3 rd digit)	Ulcerative colitis		
556.0	Ulcerative enterocolitis	K51.8 (all billable codes under K51.8)	Other UC
556.1	Ulcerative ileocolitis	K51.8 (all billable codes under K51.8)	Other UC
556.2	Ulcerative proctitis	K51.2 (all billable codes under K51.2)	Ulcerative (Chronic) Proctitis
556.3	Ulcerative proctosigmoiditis	K51.3 (all billable codes under K51.3)	Ulcerative (Chronic) Rectosigmoiditis
556.5	Left-sided ulcerative colitis	K51.5 (all billable codes under K51.5)	Left Sided Colitis
556.6	556.6 Universal ulcerative colitis		Ulcerative (Chronic) Pancolitis
556.8	Other ulcerative colitis	K51.8 (all billable codes under K51.8)	Other Ulcerative Colitis
556.9	Ulcerative colitis, unspecified	K51.9 (all billable codes under K51.9)	Ulcerative Colitis, Unspecified

Table 1. ICD Codes for UC Diagnoses within MarketScan Database

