9.2.1.2.2. Cohort 2 (Biologics cohort): Adult UC Patients Treated with Biologics

- 1. Initiation of biologic therapy (i.e. first prescription for a specific TNFi or non-TNFi agent) as captured in Marketscan since 30 May 2018
- 2. Patients with either 1 UC diagnosis code from an inpatient visit or ≥2 of any of the ICD-10 codes for UC in Table 1 from an outpatient visit prior to index date (i.e. date of first prescription for a specific biologic agent; at least one of the two required diagnoses from outpatient visits must be made by a gastrointestinal specialist)

Patients in this cohort will be assessed overall, and independently stratified by TNFi and non-TNFi use. Patients may also be on immunomodulators/immunosuppressants concurrently.

9.2.1.2.3. Cohort 3 (Immunomodulators/immunosuppressants cohort): Adult UC Patients Treated with Immunomodulators/Immunosuppressants without concurrent Biologics

- 1. Initiation of immunomodulator/immunosuppressant therapy (i.e. first prescription for a specific immunomodulator/immunosuppressant agent) as captured in Marketscan since 30 May 2018 (without concurrent biologics)
- 2. Patients with either 1 UC diagnosis code from an inpatient visit or ≥2 of any of the ICD-10 codes for UC in Table 1 from an outpatient visit prior to index date (i.e. date of first prescription for an immunomodulator/immunosuppressant agent; at least one of the two required diagnoses from outpatient visits must be made by a gastrointestinal specialist)

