9.2.2. Exclusion Criteria

To assess to facitinib utilization patterns, no exclusion criteria will be applied. However, for the active surveillance population which will consist of a subset of the study population, patients not meeting the inclusion criteria for any of the respective cohorts described above will be excluded.

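### Cohorts 2 and 3 anchor the first prescription to 30 May 2018 with no drug-free look-back, so read literally they admit patients already on treatment as initiators

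*Protocol*

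**What the plan says.** Protocol Section 9.3.4.2 sets the Cohort 2 index at the "date of first prescription for a specific biologic agent since 30 May 2018" and the Cohort 3 index at the "date of first prescription for a specific immunomodulator/immunosuppressant agent since 30 May 2018", in each case after a UC diagnosis. The inclusion criteria match. Section 9.2.1.2.2 has "Initiation of biologic therapy (i.e. first prescription for a specific TNFi or non-TNFi agent) as captured in Marketscan since 30 May 2018". Section 9.2.1.2.3 has "first prescription for a specific immunomodulator/immunosuppressant agent) as captured in Marketscan since 30 May 2018 (without concurrent biologics", where the added condition concerns biologics and not earlier use of the index agent.

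Two other rules could have screened out existing users:
- Section 9.2.1.2: "At least 12 months of continuous (i.e., no more than a 30-day gap) database enrollment before index date is required to enable analysis" of baseline characteristics. It does not say that those months must be free of the drug.
- Section 9.2.2: "patients not meeting the inclusion criteria for any of the respective cohorts described above will be excluded". No exclusion for prior use is added.

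Section 9.2.1.2 describes Sections 9.3.4.2 and 9.3.5 as the formal definitions of index date and start of follow-up. It leaves exposure measurement, such as permitted gaps between prescriptions, to the SAP.

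**The concern.** Table 2 of the protocol gives 30 May 2018 as the date tofacitinib was approved for UC. For a biologic, azathioprine, mercaptopurine or methotrexate it is just a calendar date. A patient treated with one of these for years has a first prescription since that date at the next refill or infusion, and the literal rule indexes the patient there.

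Section 9.3.5 starts follow-up at the index date and the acute risk window at drug initiation, treating the two as the same moment. For a patient already on treatment they differ, possibly by years. Section 9.7.2 reports crude rates and removes patients with a baseline history of the outcome, so existing users enter as people who have stayed on the drug free of the event. Their 12-month baseline period is also time on the drug.

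Cohort 1 has the same wording but little room for the problem, because earlier tofacitinib use can only have been for RA, for PsA or off label. The mixing of new and existing users therefore falls mainly on the cohorts that are there to put the tofacitinib rates in context.

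**Working it through.** **Text check**

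| Item | Protocol section | Look-back for the agent stated? |
|---|---|---|
| Cohort 2 initiation and index | 9.2.1.2.2, 9.3.4.2 | No; tied to 30 May 2018 |
| Cohort 3 initiation and index | 9.2.1.2.3, 9.3.4.2 | No; tied to 30 May 2018 |
| 12-month enrolment | 9.2.1.2 | No; serves baseline description |
| Exclusions | 9.2.2 | No |
| Cohort 4 naive status | 9.2.1.2.4 | Yes; all available data |
| Prior TNFi use | 9.3.1 | Yes; all available data |
| Duration of tofacitinib therapy | 9.3.3 | Counted from the first ever prescription |

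Where the protocol wants full history it says so. The Cohort 2 and 3 rules do not.

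**Who gets in.** Mainly patients on the drug on 30 May 2018. Someone who joins the database later while on treatment has a first captured prescription with less than 12 months of prior enrolment and fails that rule.

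**Illustration of size.** The protocol states no figure for Cohorts 2 and 3, so there is nothing to reproduce. From the documents: the window 30 May 2018 to 30 June 2025 is 2,588 days, so W = 2588/365.25 = 7.09 years. Assumptions, not from the documents: a constant start rate, exponential time on drug with mean D years, steady state on 30 May 2018, everyone otherwise eligible, and an event rate in the first e = 0.5 years on drug that is twice the later rate.

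Per unit start rate, the pool on drug at the start is D and new starts number W.
- Prevalent share of patients = D/(D + W). For D = 0.5: 0.5/7.59 = 7%. For D = 5: 5/12.09 = 41%.
- On-drug person-time in the window: prevalent P = D²(1 − exp(−W/D)); new N = DW − P. Prevalent share of person-time = P/(DW).
- Let x = 1 − exp(−e/D). Early person-time of new starters: E = (W − e)Dx + De − D²x. Early person-time of prevalent users: D[Dx − e·exp(−e/D)]. The two sum to WDx, so the early fraction in the mixed cohort is x.
- In units of the later rate, the true-starter rate is 1 + E/N and the mixed-cohort rate is 1 + x.

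| D (years) | Prevalent patients | Prevalent person-time | 1 + E/N | 1 + x | Ratio | Mixed rate lower by |
|---|---|---|---|---|---|---|
| 0.5 | 7% | 7% | 1.660 | 1.632 | 0.983 | 2% |
| 1 | 12% | 14% | 1.443 | 1.393 | 0.966 | 3% |
| 2 | 22% | 27% | 1.294 | 1.221 | 0.943 | 6% |
| 3 | 30% | 38% | 1.240 | 1.154 | 0.930 | 7% |
| 5 | 41% | 54% | 1.197 | 1.095 | 0.915 | 9% |

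At the first interim report date (30 June 2022) the window is 4.08 years, and the prevalent share of patients runs from 0.5/4.58 = 11% to 5/9.08 = 55%.

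With a drug-free look-back for the same agent, continuous users on 30 May 2018 no longer qualify and their share falls to about zero.

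**The case against.** The strongest answer is that the text allows a new-user reading. In Section 9.2.1.2.2 the bracket that defines initiation closes before the date, so the date may only limit when a genuine initiation counts. Item 2 for each of these cohorts describes the index date with no calendar anchor. The protocol refers repeatedly to patients who initiate or start a new therapy, and a refill is neither. This stands as evidence of intent. It does not settle the rule, because Section 9.3.4.2, named as the formal definition, attaches the date directly to the first prescription and states no look-back.

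A second answer is that look-back length and claim types belong in the SAP, which is not shown and may contain a washout. That is fair for the detail. The index date itself, however, is fixed in the protocol and not deferred, so an SAP washout would have to be reconciled with it.

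A reader might also infer that acute rates in Cohorts 2 and 3 are necessarily understated and tofacitinib made to look worse. The documents do not support that. An early high-risk period is an assumption: Section 9.3.5 says only that acute risk may be raised on drug and subside after stopping. For malignancy, followed as once exposed always at risk, longer earlier exposure could push the rate up. Nor do the documents support supposing that half or more of the final cohorts are existing users.

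**Conclusion.** The concern holds as a defect in the stated rule: the operative definition for Cohorts 2 and 3 departs from the protocol's own intention to study initiators. Taken literally it admits mainly patients on drug on 30 May 2018, and so mixes new and prevalent users in the contextualization cohorts but hardly in Cohort 1.

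The 7% to 41% share of patients and the 2% to 9% lower crude on-drug rate rest wholly on the steady-state, exponential-duration and twofold-early-rate assumptions. They show a plausible order of size for one outcome pattern, and other outcomes could move differently.

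The point should be fixed, but it does not undermine the primary objective. A reader might infer that the main malignancy result is compromised. It is not: that estimate concerns Cohort 1 and is little affected, the other cohorts serve as context, and no hypothesis is tested.

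**What to change.** In Sections 9.2.1.2.1 to 9.2.1.2.3 and 9.3.4.2, define initiation as the earliest dispensing or administration on or after 30 May 2018 with no pharmacy or administration claim for the same agent in the preceding 12 months of required enrolment. Apply it to Cohorts 1 to 3, and repeat the analysis with all available data as the look-back, as a sensitivity analysis. Report how many patients the criterion removes from each cohort. If the SAP already holds a washout, align the two documents.

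The look-back data are already required, so no new data are needed. The costs are smaller Cohorts 2 and 3 and a possible break with the interim reports, which Section 6 scheduled for 30 June 2022 and 30 June 2024, both before version 3.0 of 30 September 2024. The final report should state any such break.

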Patients may switch between the tofacitinib and contextualization cohorts over time if inclusion/exclusion criteria listed below are met. Additionally, patients will be eligible for entry into a particular cohort each time they start a new therapy within the same drug class. For acute endpoints, patients will be censored from a particular cohort when they start a new therapy in a different drug class. For the endpoint of MACE, for example, patients in Cohort 1 (UC patients initiating treatment with tofacitinib) will be censored if and when they switch to a specific biologic agent, but will be eligible for subsequent inclusion into Cohort 2 (patients initiating treatment with biologics). For non-acute outcomes such as malignancy and death, outcomes will be evaluated using a "once exposed always at risk" paradigm (as described in Section 9.3.5).

Formal definitions of index dates/start of follow-up are provided in Sections 9.3.4.2 and 9.3.5.Details of exposure measurement (e.g., allowing specified gaps between prescriptions in continuous exposure, etc.) will be detailed in the statistical analysis plan (SAP).

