9.3.5. Follow-up in the active surveillance population

Patients in the active surveillance population will be followed from index date until first occurrence of each outcome of interest, treatment switch or discontinuation, with the appropriate outcome-specific extension to exposure (i.e. 90 day window for acute events, and "once-exposed always at risk" approach for non-acute events like malignancy as described below), and with death, lost medical/pharmacy coverage, and end of data collection (30 June 2025) treated as censoring events.

Acute events of interest in this study are thought to potentially occur at a higher rate while on drug, but that increased risk subsides after the drug is discontinued (i.e., serious and opportunistic infections, herpes zoster reactivation, MACE, VTE, GI perforation, PML). These events will be evaluated over a risk window that includes time from drug initiation until 90 days after end of treatment. When a patient initiates a new therapy within the 90-day

[figure not shown]
extension, the time and events during the overlapping period will be assigned to both treatments. An example of the as-treated approach with the 90-day extension period is provided in the scenario illustrated below.

------ represents risk period counted
+++++ represents time not included in the risk period
x represents occurrence of an acute safety event of interest such as MACE
) represents drug discontinuation
| represents tofacitinib initiation
| represents biologic initiation
| represents 90-day extension period

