In the above scenario, the patient has two biologic initiations and a tofacitinib initiation. The initiation of tofacitinib therapy occurs within the 90-day extension period for the first biologic. Thus, the time and event during the overlapping period will be assigned to both the first biologic and tofacitinib. Specifically, for the first biologic initiation, a safety event occurred within the 90-day extension period, and exposure time is counted from the time of drug initiation (Index date 1) until the occurrence of the safety event. For the tofacitinib initiation, one safety event occurred and exposure time is counted from Index date 2 (date of initiation of tofacitinib which occurs within the 90-day extension period of the first biologic initiation) to the occurrence of the safety event (which also occurred within the 90-day extension period for the first biologic). Tofacitinib treatment was discontinued when the safety event occurred, and there is a period of time where no treatment is used. For the second biologic initiation, one safety event occurred and exposure time is counted from Index date 3 to the safety event.

For the purpose of analysis, the patient has 2 biologic initiations and a tofacitinib initiation:

A sensitivity analysis whereby if a new medication is started during the 90-day window after discontinuation of a previous medication, initiation of the new medication will stop the 90-day risk window, and any event prior to the new medication start will be assigned to the discontinued medication will also be conducted and further discussed in the SAP. The 90-day extension period is implemented in part to accommodate ongoing exposure to treatments with longer half-lives, and in part to ensure that any subclinical or undiagnosed illness at time of end of treatment is captured. For each patient, follow-up time contributing to one of the three treated cohorts will be calculated as the sum of dispensed medication days (based on days supply) plus the 90-day extension period.

For NMSC and malignancies, surgery for UC, and death (and as a sensitivity analysis for PML), the occurrences of which are expected to be delayed relative to the time of exposure, the outcomes will be evaluated from drug initiation until the first event or loss to follow up, reflecting a "once-exposed always at risk" paradigm. If a patient switches to a new drug, the subsequent observation time will contribute to multiple therapies.

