9.7.2. Analysis of safety endpoints of interest

For the safety endpoints of interest, descriptive statistics, counts and proportions, cumulative incidence proportions, and crude incidence rates (i.e., number of events per person-years) and associated two-sided 95% confidence intervals will be calculated as appropriate. UC patients with a baseline history of an outcome of interest will be excluded from the calculation of the incidence rate for that particular outcome of interest (e.g. patients with a baseline history of malignancy will be excluded from the calculation of the incidence rate for malignancy).

Several subgroup analyses will be performed. These include (but are not limited to) stratification by:

- Tofacitinib dose (5 mg twice daily vs. 11 mg once daily vs. 10 mg twice daily vs. 22 mg once daily)
- Patient characteristics such as age at index date, including a subgroup analysis of patients <50 years vs. ≥50 years, and patients <65 years vs. ≥65 years
- For the outcomes of VTE and MACE, subgroup analysis of patients with ≥1 thrombosis risk factors (as defined in Section 9.3.1.1) vs. no thrombosis risk factors, and
- Key indicators of disease severity such as number of previous biologic treatments (i.e. prior biologic use vs. none; among those with prior biologic use, 1st biologic vs. 2nd biologic vs. ≥3 biologics)

This will be a time to first event analysis based on an index date defined for each cohort with appropriate censoring rules applied (based on therapy switches, end of study, etc.) for those

who do not experience an event by end of follow-up period. Rates will be expressed as the number of events/100 person-years of follow-up.

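### Index dates per initiation, plus malignancy follow-up that stays open after a switch, let one patient's person-time and event enter the overall Cohort 2 or 3 rate more than once, and no counting rule prevents it

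*Protocol*

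**What the plan says.** Four statements in the protocol combine.

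- **Re-entry (9.2.1.2):** "patients will be eligible for entry into a particular cohort each time they start a new therapy within the same drug class".
- **Index dates (9.3.4.2):** for Cohort 2, "For patients with more than one biologic initiation, more than one index date will be defined (e.g., one for each biologic initiation"; for Cohort 3, "For patients with more than one immunomodulator/immunosuppressant initiation, more than one index date will be defined". Cohort 1 has one index date, the first tofacitinib prescription.
- **Non-acute outcomes (9.3.5):** for NMSC and malignancies, surgery for UC and death, "the outcomes will be evaluated from drug initiation until the first event or loss to follow up". On overlap: "If a patient switches to a new drug, the subsequent observation time will contribute to multiple therapies".
- **Acute outcomes (9.3.5):** follow-up ends 90 days after treatment. If a new therapy starts within those 90 days, "the time and events during the overlapping period will be assigned to both treatments".

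Section 8 asks for the Cohort 2 rate overall as well as by TNFi/non-TNFi class and by number of earlier biologics. Section 9.7.2 says that "crude incidence rates (i.e., number of events per person-years) and associated two-sided 95% confidence intervals will be calculated as appropriate". The same section describes a time-to-first-event analysis that starts from one index date per cohort (singular).

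**The concern.** Take a patient who starts three biologics and is then diagnosed with cancer. Under 9.3.4.2 the patient has three index dates in Cohort 2. Under 9.3.5 neither switch ends the earlier malignancy follow-up, so the cancer lies in three open risk windows of the same cohort. All calendar time after the third start is also present three times.

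The other rules do not remove the copies. Follow-up for an outcome stops at the event, but the event ends all three windows together. The baseline-history exclusion does not help either, because the cancer comes after every index date.

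Two things are at stake. The overall rate becomes an average over initiations, so patients with many starts weigh more. And an interval that treats the copies as independent events overstates precision. Cohorts 2 and 3 are the context for the tofacitinib malignancy rate. Cohort 1 would count each patient once while its context counts some patients two or three times.

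**Working it through.** The protocol states no rate, event count, switching pattern or interval method for these cohorts, so there is no figure to reproduce. Every numerical input below is an assumption.

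**Formula.** Let each true event appear in *k* records, and its person-time likewise. With a Poisson number of true events D, the recorded count has variance E[D]·E[k²], while an ordinary Poisson interval uses E[D]·E[k]. Hence:

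- variance inflation V = E[k²]/E[k]
- ratio of ordinary to correct interval width = 1/√V
- approximate coverage = 2Φ(1.96/√V) − 1

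**Worked case.** Assume 60/25/15% of patients have 1/2/3 starts at years 0/1/2, with four years of follow-up and a constant hazard, so that events are spread almost evenly over the four years.

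- Two starts: k = 1 in the first year and 2 afterwards. E[k] = 0.25·1 + 0.75·2 = 1.75; E[k²] = 0.25·1 + 0.75·4 = 3.25.
- Three starts: E[k] = 0.25·1 + 0.25·2 + 0.5·3 = 2.25; E[k²] = 0.25·1 + 0.25·4 + 0.5·9 = 5.75.
- Overall: E[k] = 0.6 + 0.25·1.75 + 0.15·2.25 = 1.375; E[k²] = 0.6 + 0.25·3.25 + 0.15·5.75 = 2.275.
- V = 2.275/1.375 = 1.65; width ratio 0.78; coverage about 87%.

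A simulation of this case (2,000 patients, 0.8 malignancies per 100 person-years, exact Poisson interval) agrees. On average 63 true events become 86 records, and 7,873 person-years become 10,811. Coverage is 88%, against 96% when each patient is counted once. The ordinary standard error is 0.77 of the true one.

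**Point estimate.** 63/7,873 and 86/10,811 are both 0.80 per 100 person-years, so the rate is not multiplied. The weights do move: multi-starters are 40% of patients here but supply 1 − 0.6/1.375 = 56% of recorded person-time. If their risk differs, the overall rate moves toward theirs.

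**Range for coverage of an ordinary Poisson interval, by simulation:**

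| Assumed pattern | Coverage |
|---|---|
| Everyone has 2 or 3 starts (3,000 patients, 1 per 100 person-years, follow-up 0.5 to 7.08 years) | 82% |
| Same setting, 40% with 2 or 3 starts | 89% |
| Same setting, 20% with 2 or 3 starts | 92% (91.5%) |
| 60/25/15% with 1/2/3 starts, four full years, 2,000 patients | 88% |
| 80/15/5%, four full years, 2,000 patients | 92% |
| 80/15/5%, with disenrolment of 0.3 per year | 93% |
| 80/15/5%, with disenrolment of 0.5 per year | 94% |

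The formula's extreme, every event counted three times, gives V = 3 and 74%. That is a limit rather than a realistic case.

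**Rising hazard.** In the 3,000-patient setting, a constant hazard gave no bias (1.00 against 1.00 per 100 person-years). A hazard rising each year by 30% of its starting value moved the rate from 1.69 to 1.73, 1.70 to 1.76 and 1.70 to 1.82 with 20%, 40% and 100% multi-starters. That is about 2% to 8% too high.

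**The case against.** The strongest reply is that the protocol never says the overall Cohort 2 rate is the sum of all index-date records. Double assignment is stated per therapy. Section 9.7.2 uses a singular index date per cohort, and a sentence in 9.3.5 computes follow-up per patient within a treated cohort. This stands in part: the duplication follows from the stated rules but is not announced. On the other side, the worked example in 9.3.5 takes two biologic records from one patient, each with its own exposure time and event, so several records per patient in one cohort is the protocol's own illustration. If 9.7.2 means one record per patient, it contradicts 9.2.1.2 and 9.3.4.2. Either way the sections need reconciling.

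The second reply is that the interval method belongs in the SAP. That is correct, and its absence is not the complaint. But the counting unit is already set in the protocol, and a later choice of variance does not decide whether the overall rate counts patients or initiations.

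Three stronger readings are tempting, and the documents do not support them:

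- *That the malignancy rate is inflated two- or three-fold.* Numerator and denominator are duplicated together.
- *That the reported intervals will certainly be too narrow.* This holds for an ordinary Poisson or exact interval, and the protocol names none.
- *That acute outcomes suffer equally.* Their overlap is confined to the 90-day extension, and 9.3.5 plans a sensitivity analysis that closes the window at the new start. No such analysis is described for malignancy.

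Finally, the study is descriptive, without hypotheses, and initiation-level records are needed for the line-of-therapy strata. This limits the severity but does not remove the problem in the overall rates.

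**Conclusion.** The point holds in limited form. Sections 9.2.1.2, 9.3.4.2 and 9.3.5 together allow the same person-time and the same malignancy, NMSC, surgery or death to enter the overall or class-level rate of Cohort 2 or 3 more than once. Section 9.7.2 points the other way, and nothing settles which applies.

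If all records are pooled, the crude rate leans toward patients with several starts; how far it moves depends on how their risk differs or changes with time. An ordinary 95% interval would cover roughly 82% to 94%. These figures rest on assumed switching, hazard and enrolment patterns. With few switchers and short enrolment the loss is small.

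The primary objective, the Cohort 1 malignancy rate, is untouched. Severity is moderate: the flaw affects the weighting and stated precision of the contextual rates.

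**What to change.** In 9.3.5 and 9.7.2, state that for every overall and class-level rate in Cohorts 2 and 3 a patient's overlapping episodes are merged, so that each day and each first event counts once per patient per cohort. Keep initiation-level records only for agent or line-of-therapy strata. Wherever a patient contributes more than one record, use a patient-clustered interval (robust variance or a bootstrap that resamples patients). Align the index-date wording in 9.7.2 with 9.3.4.2.

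The cost is a few sentences and minor programming, with no new data. Intervals for Cohorts 2 and 3 will be somewhat wider than ordinary Poisson intervals on pooled records.

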9.2.1.2.4. Cohort 4 (Naive cohort): Biologic/immunomodulator/immunosuppressantnaïve Cohort

- 1. Naive to biologics/immunomodulators/immunosuppressants using all available data
- 2. Patients with either 1 UC diagnosis code from an inpatient visit or ≥2 of any of the ICD-10 codes for UC in Table 1 before start of follow-up (at least one of the two required diagnoses from outpatient visits must be made by a gastrointestinal

specialist). For these patients, start of follow-up will be defined by an index date as described in Section 9.3.4.2.

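### The protocol contradicts itself on when Cohort 4 follow-up starts, and no rule keeps outcomes in a qualifying hospital stay out of that cohort's incidence rates

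*Protocol*

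**What the plan says.** Section 9.2.1.2.4 admits to Cohort 4 "Patients with either 1 UC diagnosis code from an inpatient visit", or those with two or more codes under the outpatient rule. The wording on timing is "ICD-10 codes for UC in Table 1 before start of follow-up". The same item adds that "start of follow-up will be defined by an index date as described in Section 9.3.4.2".

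Section 9.3.4.2 then defines the Cohort 4 index date: "This will be the date of UC diagnosis as described in Section 9.2.1.2.4, since 30 May 2018". For Cohorts 1 to 3 the index date is instead a first prescription that follows the UC diagnosis.

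Section 9.3.5 states: "Patients in the active surveillance population will be followed from index date until first occurrence of each outcome of interest". It gives no lag, next-day start or discharge rule.

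Section 9.7.2 contains the only filter for events that are not incident: "UC patients with a baseline history of an outcome of interest will be excluded from the calculation of the incidence rate for that particular outcome". Section 9.3.1 sets the look-back for that history relative to the index date (12 months, or ever for malignancy) and does not say whether the index day or an index hospital stay belongs to it.

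These definitions are not deferred to the SAP. Section 9.2.1.2 says: "Formal definitions of index dates/start of follow-up are provided in Sections 9.3.4.2 and 9.3.5".

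**The concern.** In Cohort 4 the claim that establishes eligibility also starts the clock. For a patient who enters by one inpatient code, eligibility, time zero and a hospital stay coincide. The stay need not be for UC: an admission for an infarction or a cancer operation that also carries a UC code would qualify.

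If outcomes recorded in that stay are counted, each adds one event and almost no person-time. The rates are crude, so no later step in the analysis corrects this. Cohorts 1 to 3 start at a later prescription, so their qualifying code does not itself open follow-up. Section 8 expects Cohort 4 to have milder disease than the other cohorts. An upward error confined to Cohort 4 would blur the context it is meant to give.

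**Working it through.** **Does the text settle the start date?**

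1. Section 9.2.1.2.4: the qualifying code or codes precede the start of follow-up.
2. The same section: start of follow-up is the index date of Section 9.3.4.2.
3. Section 9.3.4.2: that index date is the date of UC diagnosis. Section 9.3.1, when defining years since diagnosis, dates diagnosis at the first inpatient code or the second outpatient code, which is the code that completes eligibility.

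Steps 2 and 3 put the start of follow-up on the date of the completing code. Step 1 puts that code earlier. The definitions are inconsistent for both entry routes.

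**Which events in a qualifying inpatient stay would count?**

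| Event in the stay | Code dated at or near admission | Code dated at discharge |
|---|---|---|
| Serious infection, VTE, MI, perforation, UC surgery, malignancy | On or after index, so counted unless a rule removes it | Mostly before index, so baseline history under 9.7.2; an event on the index day is unresolved |
| In-hospital death | After index, so counted | Falls on the index day and cannot be baseline history, so it could be counted |

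Patients who qualify by two outpatient codes have no qualifying stay.

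**How large could the effect be?** The protocol gives no Cohort 4 rate, event count or inpatient share, so there is no figure to reproduce. The 59,080 UC patients in Section 9.5 are not split by route and are not a Cohort 4 count. The following is illustration only, and every input is an assumption:

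- p = share of Cohort 4 entering by an inpatient code: 5% to 30%
- q = risk that a given outcome is recorded in the qualifying stay: 0.5% to 5%
- λ = true rate after the stay: 0.3, 1.0 or 3.0 per 100 person-years
- T = follow-up: 2 years, with a constant hazard

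Per patient, when stay events are counted:

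- events = (1 − pq)(1 − e^(−λT)) + pq
- person-years = (1 − pq)(1 − e^(−λT)) / λ
- observed rate = events / person-years

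Example with p = 15%, q = 2%, λ = 0.01 per year and T = 2:

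- pq = 0.003, and 1 − e^(−0.02) = 0.019801
- events = 0.997 × 0.019801 + 0.003 = 0.022742
- person-years = 0.997 × 0.019801 / 0.01 = 1.97419
- rate = 0.022742 / 1.97419 = 1.152 per 100 person-years, a ratio of 1.15

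Over the assumed range at T = 2 (rate per 100 person-years, ratio in brackets):

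| λ | p 5%, q 0.5% | p 15%, q 2% | p 30%, q 5% |
|---|---|---|---|
| 0.3 | 0.313 (1.04) | 0.451 (1.50) | 1.064 (3.55) |
| 1.0 | 1.013 (1.01) | 1.152 (1.15) | 1.769 (1.77) |
| 3.0 | 3.013 (1.00) | 3.155 (1.05) | 3.784 (1.26) |

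The effect shrinks with longer follow-up. With λ = 1.0, p = 15% and q = 2%, the rate is 1.30, 1.15, 1.08 and 1.04 at T = 1, 2, 4 and 7.08 years. The last value is the longest possible follow-up, 30 May 2018 to 30 June 2025.

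If stay events are not counted, pq leaves the numerator and the rate returns to λ.

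**The case against.** The strongest reply is that inflation is not shown. With discharge dating, most events in the stay precede the index date and fall under the baseline-history exclusion. Read literally, Section 9.2.1.2.4 also forbids follow-up from starting on the qualifying date. Section 9.3.1 leaves the index day open, and Section 9.3 defers code and variable definitions to the SAP. This stands in part: the bias is conditional. It does not remove the contradiction, because Section 9.2.1.2 places the index-date definitions in the protocol. Nor does it settle an in-hospital death, which could count under either dating.

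A second reply concerns the stakes. A reader might infer that the plan inflates the naive cohort's rates throughout and so makes tofacitinib look safer against its reference group. The documents do not support that. Only inpatient-route entrants are exposed, and their share is not given. Cohort 4 is one of several contextualization cohorts, the study is descriptive with no prior hypotheses (Section 9.1), and Section 9.7.4 centres the final report on tofacitinib and biologics. Section 8 already says that Cohort 4 differs in severity.

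A third reply concerns the remedy. Starting after discharge conditions entry on surviving the stay, and it drops first-admission colectomies, which are real outcomes of untreated UC. This stands, and the fix must allow for it.

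**Conclusion.** The point holds as an internal contradiction with a missing rule. Sections 9.2.1.2.4 and 9.3.4.2 disagree on whether the qualifying diagnosis precedes or starts Cohort 4 follow-up. Nothing dates an inpatient diagnosis or says what happens to outcomes in the qualifying stay.

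Where stay events are counted, the error in Cohort 4's crude rates is upward, greatest for rare outcomes and short follow-up. That rests on the inpatient diagnosis being dated at or near admission, or on the event being an in-hospital death in that stay. The magnitude is unknown: the illustration runs from negligible to more than threefold, and no single value in it should be taken as an estimate. The primary objective, the malignancy rate in tofacitinib initiators, does not depend on it. The change is worth making because the ambiguity alters a numerator and is cheap to remove.

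**What to change.** - In Section 9.3.4.2, start Cohort 4 risk time the day after discharge when the qualifying code is inpatient, or the day after the outpatient code that completes the definition.
- Reword Section 9.2.1.2.4 to match, so that the qualifying codes do precede follow-up.
- In Section 9.7.2, state that for Cohort 4 outcomes coded up to the day before risk time starts, including any in the qualifying stay, are baseline history for that outcome.
- Report qualifying-stay colectomies and in-hospital deaths separately, or add a sensitivity analysis that counts all qualifying-stay events and gives the number of inpatient-route entrants.

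The cost is a few sentences in the protocol, matching SAP text and one extra table, with no new data. Cohort 4 loses the days of the stay. For each outcome it also loses the patients whose stay contained it: under the assumed ranges, pq runs from 0.05 × 0.005 = 0.025% to 0.30 × 0.05 = 1.5% of the cohort. The main death and surgery rates will then describe patients who left the qualifying stay alive, and the report should say so.
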